3.5 Covariates definition and measurement

Baseline comorbidities will be ascertained by examining inpatient and outpatient hospital diagnoses in the ten years preceding study enrolment and recorded in the Danish National Registry of Patients in Denmark and in the GPRD's Event File in the UK. We will use the Charlson comorbidity index to summarise comorbidities (other than diabetes) in the analysis.¹⁹

Use of prescription medication other than oral glucose lowering therapy will be ascertained based on prescription history (AUPD in Denmark; Drug File in the GPRD). Concomitant use will be defined as a record of at least one prescription for a medication that falls in one of the categories listed below between the first and the last prescription for glucose lowering therapy.

- Lipid-lowering agents (statins);

- Antihypertensive agents (ACE inhibitors, angiotensin receptor blockers, beta-blockers, calcium-channel blockers);
- Diuretics (loop, potassium sparing, thiazide);
- Nitrates;
- Antiplatelet agents.

Smoking, alcoholism, and body mass index (BMI) are available for about 70% of the patients in the GPRD's Additional Clinical Detail File (for the UK). In Denmark, these data are not generally recorded in registries, although there are diagnostic codes for obesity and alcoholism, which we will use to identify patients who were hospitalised. It may be possible to obtain data on smoking, body mass index and blood pressure at least on some members of the study population via linkage to the National Indicator Project and Danish Registry of Patients. The size of subgroup with available data on smoking, alcoholism, and BMI will not be known until data linkage.

Age and sex of the patients: in Denmark, date of birth and sex are encoded in the unique identifier that will be used to link the data; in the UK, the GPRD records the demographic data in the Registration File.

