type2	250.01-250.05; 250.08	E11.2-E11.8
Any tumor	140-194	C00-C75
Leukemia	204-207	C91-C95
Lymphoma	200-203; 275.59	C81-C85; C88; C90; C96
Moderate to severe liver disease	070.00; 070.02; 070.04; 070.06; 070.08; 573.00; 456.00-456.09	B15.0; B16.0; B16.2; B19.0; K70.4; K72; K76.6; I85
Metastatic solid tumor	195-198; 199	C76-C80
AIDS	079.83	B21-B24

Anatomical Therapeutic Chemical (ATC) codes used to abstract the Aarhus University Prescription Database

Drug	ATC code
Drugs used in diabetes	A10
Insulins and analogues for injection, fast-acting	A10AB
Insulins and analogues for injection, intermediate-acting	A10AC
Insulins and analogues for injection, intermediate-acting combined with fast-acting	A10AD
Insulins and analogues for injection, long-acting	A10AE
Insulins and analogues for inhalation	A10AF
Rosiglitazone preparations	A10BG02 rosiglitazone A10BD03 rosiglitazone+metformin A10BD04 rosiglitazone+glimepiride
Biguanides	A10BA
Sulfonamides, urea derivatives	A10BB
Sulfonamides (heterocyclic)	A10BC
Combinations of oral blood glucose lowering drugs	A10BD (except A10BD03 and A10BD04)
Thiazolidinediones other than rosiglitazone	A10BG03 (pioglitazone)
Alpha glucosidase inhibitors	A10BF
Dipeptidyl peptidase 4 (DPP-4) inhibitors	A10BH
Other blood glucose lowering drugs, excl. insulins	A10BX
Lipid-lowering drugs including statins	C10A
Antihypertensive agents	C07 (beta blockers) C08 (calcium channel blockers) C09, C09 (ACE-inhibitors and angiotensin blockers)
Diuretics (loop, potassium sparing, thiazide)	C03
Nitrates	C01DA
Antiplatelet agents (anti-thrombotic)	B01A

ATC classification: http://www.whocc.no/atc_ddd_index/

Codes used to identify laboratory tests according to the International Union of Pure and Applied Chemistry (IUPAC)

Test	IUPAC codes
Fasting blood glucose	ASS00203, ASS00204, DNK35842, NPU02193, NPU02195, NPU08509, NPU08972, NPU22069
HbA1c	NPU02307, NPU03835
Haemoglobin (anaemia)	NPU02319, AAA00359, AAA00137, AAA00115
Alanintransaminase	DNK05051, NPU19651
Albumin/creatinine ratio (urine)	ASS00023, ASS00024, ASS00194, AAA00760, DNK05289, NPU03918, NPU03929, 10913
Serum creatinine	NPU18016, NPU01807
Total cholesterol	NPU01566
LDL cholesterol	NPU01568, NPU10171
HDL cholesterol	NPU01567, NPU10157
Triglycerides	NPU03620

IUPAC codes: <http://www.sst.dk/NPU>

Diagnostic codes used to abstract the General Practice Research Database**Diabetes (includes both non-specific and Type II)**

13AB.00 DIABETIC LIPID LOWERING DIET

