 5776 QUINAPRIL
 4584 Benazepril

ACE-inhibitor combinations

4618 PERINDOPRIL + INDAPAMIDE

ACE-inhibitors and diuretics

4569 CAPTOPRIL W HYDROCHLORTH
 4577 LISINOPRIL W HYDROCHLORO
 4581 ENALAPRIL W HYDROCHLOROT
 4590 benazepril hydrochlorothiazide

ACE-inhibitors and calcium channel blockers

4598 FELODIPINE+RAMIPRIL

Angiotensin II antagonists

4589 LOSARTAN
 4596 VALSARTAN
 4615 TELMISARTAN
 4617 EPROSARTAN
 6202 AMIAS (=Candesartan)
 6203 APROVEL (= Irbesartan)
 24518 OLMESARTAN MEDOXOMIL

Angiotensin II inhibitors and diuretics

4595 COZAAR-COMP
 6207 IRBESARTAN+HYDROCHLOROTH

Beta-blockers incl. Combination with diuretics

1320 ACEBUTOLOL HCL
 1321 TIMOLOL MALEATE
 1326 ATENOLOL
 4561 ATENOLOL W CHLORTHALIDON
 4562 NADOLOL W BENDROFLUMETHI
 4568 ATENOLOL W NIFEDIPINE
 4583 CELIPROLOL
 4611 NEBIVOLOL
 5710 PROPRANOLOL
 5723 OXPRENOLOL HCL
 5732 PINDOLOL
 5754 NADOLOL
 5757 CLOPAMIDE W PINDOLOL
 5769 BETAXOLOL
 5770 TIMOLOL,AMILORIDE,HYDROC
 5773 OXPRENOLOL W CYCLOPENTHI
 5778 ESMOLOL
 6140 METOPROLOL
 6178 PROPRANOLOL W BENDROFLUA
 6180 METOPROLOL W HYDROCHLORO
 6182 METOPROLOL W CHLORTHALID
 6184 SOTALOL W HYDROCHLOROTHI
 6185 TIMOLOL W BENDROFLUAZIDE
 6188 BISOPROLOL FUMARATE
 6191 CARTEOLOL HCL TABLETS
 6196 BISOPROLOLFUMARATE W HYD
 6798 AMILORIDE,ATENOLOL,HYDRO
 16704 FUROSEMIDE W PENBUTOLOL
 6164 LABETALOL HCL
 6166 SOTALOL HCL
 6198 CARVEDILOL
 6797 HYDROCHLOROTHIAZIDE W AC
 4594 TENBEN
 4599 HYDROCHLOROTHIAZIDE+TIMO
 5731 alprenolol
 6160 bupranolol hcl

1327 penbutolol
16704 furosemide w penbutolol

Calcium channel blockers

4579 FELODIPINE SR
4587 LACIDIPINE
4591 DILTIAEM + HYDROCHLOROT
4597 NISOLDIPINE
4598 FELODIPINE+RAMIPRIL
4607 ISRADIPINE
5733 VERAPAMIL
5779 VERAPAMIL HCL 180MG/2MG
6136 AMLODIPINE
6145 NIFEDIPINE
6148 PERHEXILINE MALEATE
6156 LIDOFLAZINE
6175 DILTIAZEM
6189 NIMODIPINE
6187 NICARDIPINE
6204 ZANIDIP
6205 MIBEFRADIL

Diuretics

Thiazides

6716 Bendrofluzide
4527 Benzthiazide
6746 Chlorothiazide
6734 Hydrochlorothiazide
4524 Cyclopenthiazide
6737 Polythiazide
6742 Chlorthalidone (thiazide-like)
6574 Mefruside (thiazide-like)
6770 Xipamide (thiazide-like)
6758 Metolazone
6748 Hydroflumethiazide
6764 Clopamide
16703 Clopamide with potassium
4554 Indapamide

Loop diuretics

6718 Furosemide
6756 Bumetanide
16711 Torasemide
6720 Ethacrynic acid

Kalium-sparing diuretics

6719 Triamterene
6753 Amiloride
6701 Spironolactone
6420 Metyrapone

Diuretics/combinations

6702 Acetazolamide
 16710 Bumetanide + amiloride

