 6794 Furosemide + amiloride
 6795 Furosemide + triamterene
 6785 Chlorthalidone + triamterene
 6721 Hydrochlorothiazide + triamterene
 6796 Furosemide + spironolactone
 6717 SPIRONOLACTONE W HYDROCHLOROTHIAZIDE
 6763 Spironolactone + thiazides
 6750 Amiloride + hydrochlorothiazide
 4576 Amiloride + cyclopenthiiazide

Thiazides with antihypertensives

4561 ATENOLOL W CHLORTHALIDONE
 6798 AMILORIDE,ATENOLOL,HYDROCHLOROTHIAZIDE

4594 Atenolol
 6797 Acebutolol
 6196 Bisoprolol
 4562 Nadolol
 5773 Oxprenolol
 5757 Pindolol
 5770 TIMOLOL,AMILORIDE,HYDROCHLORTHIAZIDE
 6185 Timolol
 4556 PROPRANOLOL W HYDROCHLORTHIAZIDE
 6178 Propranolol
 6180 METOPROLOL W HYDROCHLOROTHIAZIDE
 6182 Metoprolol
 6184 Sotalol
 4569 Captopril
 4581 Enalapril
 4608 Quinapril
 4577 Lisinopril
 4591 Diltiazem
 4515 RESERPINE W HYDROCHLOROTHIAZIDE PLUS
 4525 CYCLOPENTHIAZIDE W POTASSIUM CHLORIDE
 4517 METHYLCLOTHIAZIDE W DESERPIDINE
 4530 CYCLOPENTHIAZIDE,RESERPINE,POTASSIUM CHLORIDE
 4532 GUANETHIDINE,CYCLOPENTHIAZIDE,POTASSIUM CHLORIDE
 4536 HYDROFLUMETHIAZIDE,KCL,RAUWOLFIA,SERPENTHE
 4539 GUANETHIDINE W HYDROCHLOROTHIAZIDE
 4544 BUTABARBITAL,HYDROCHLOROTHIAZIDE,RESERPINE
 4552 CLONIDINE W CHLORTHIAZIDE
 4557 HYDRALAZINE W HYDROCHLOROTHIAZIDE
 4564 METHOSERPIDINE W BENZTHIAZIDE
 4582 LISINOPRIL W HYDROCHLOROTHIAZIDE
 4585 ALKAVERVIR W EPITHIAZIDE
 4590 BENAZEPRIL, HYDROCHLOROTHIAZIDE
 4599 HYDROCHLOROTHIAZIDE+TIMOLOL+AMILORIDE

4601 METHYLDOPA W HYDROCHLOROTHIAZIDE
4602 (METHYLCLOTHIAZIDE W DESERPINE
4603 METHYLDOPA W CHLOROTHIAZIDE
6146 RESERPIN,DIHYDRALAZINE,HYDROCHLOROTHIAZIDE,KCL
6207 IRBESARTAN+HYDROCHLOROTHIAZIDE
6707 HYDROCHLOROTHIAZIDE W POTASSIUM CHLORIDE
6711 BENDROFLUMETHIAZIDE W POTASSIUM CHLORIDE
6723 METHYLCLOTHIAZIDE
6728 BENDROFLUMETHIAZIDE,RAUWOLFIA SERP,KCL
6735 TRICHLORMETHIAZIDE
6736 HYDROCHLOROTHIAZIDE W MEPROBAMATE
6738 TRICHLOMETHIAZIDE W RESERPINE
6739 CHLOROTHIAZIDE W RESERPINE
6741 (GUANETHIDINE W HYDROCHLOROTHIAZIDE
6744 CYCLOTHIAZIDE W POTASSIUM CHLORIDE
6749 CYCLOTHIAZIDE
6750 HYDROCHLOROTHIAZIDE W AMILORIDE HCL
6762 POLYTHIAZIDE W RESERPINE
6771 BUTHIAZIDE
6783 (SPIRONOLACTONE W HYDROCHLOROTHIAZID
6789 TRIAMTERINE W BENZTHIAZIDE
6792 (AMILORIDE W HYDROCHLOROTHIAZIDE
9001 CRYPTENAMINE W METHYLCLOTHIAZIDE
16701 CHLOROTHIAZIDE W SPIRONOLACTONE
16702 CHLOROTHIAZIDE W SPIRONOLACTONE,LACTOSE
16709 ETHIAZIDE
40007 HYDROCHLOROTHIAZIDE OR PLACEBO STUDY
6731 QUINETHAZONE
4545 DIHYDROERG,CLOPAMIDE,RESERPINE
5758 PINDOLOL W CLOPAMIDE
6742 CHLORTHALIDONE

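### At least five UK fixed-combination codes set only one of the antihypertensive and diuretic covariates while 23 others set both, and the Danish code rows allow no product with one ATC code to set both

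*Protocol*

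**What the plan says.** Protocol section 3.5 names five groups of co-medication. Two matter here: "Antihypertensive agents (ACE inhibitors, angiotensin receptor blockers, beta-blockers, calcium-channel blockers") and the diuretics (loop, potassium-sparing and thiazide). The rule for setting each covariate is "Concomitant use will be defined as a record of at least one prescription for a medication that falls in one of the categories listed below", within the span from the first to the last glucose-lowering prescription. Nothing is said about a tablet that contains a drug from each group.

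The code lists in Appendix 1 are therefore the working definition.

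- **UK (GPRD codes).** There is an antihypertensive block (ACE inhibitors, angiotensin II antagonists, beta-blockers, calcium channel blockers and their combinations) and a diuretic block, which includes a group for thiazides combined with antihypertensives. Many combination codes are printed in both blocks. "4595 COZAAR-COMP" is printed only in the antihypertensive block. "4582 LISINOPRIL W HYDROCHLOROTHIAZIDE", "4608 Quinapril" and "4556 PROPRANOLOL W HYDROCHLORTHIAZIDE" are printed only in the diuretic block, as is 5758 (pindolol with clopamide).
- **Denmark (ATC codes).** The antihypertensive row is "C07 (beta blockers) C08 (calcium channel blockers) C09, C09 (ACE-inhibitors and angiotensin blockers"). The row "Diuretics (loop, potassium sparing, thiazide") has the single prefix C03. Section 6.1 says that the ATC classification is recorded for each dispensed drug, together with a unique product number.

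**The concern.** Where a protocol gives no combination rule, the lists should at least follow one consistently. The UK lists do not. The same pair of ingredients sets both covariates under one code and a single covariate under another, so a patient's covariate values can depend on which code the practice recorded. Denmark works differently again, because non-overlapping ATC prefixes mean that each product is assigned to one category only.

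Section 3.6.3 plans regression-based risk ratios for acute drug reactions, adjusted for confounding, and section 3.4.3 makes those reactions largely cardiovascular. Blood-pressure treatment and diuretics are plausible confounders of such outcomes. If their indicators are set wrongly for some patients, the adjustment is weaker than intended.

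**Working it through.** The protocol states no count on this point, so there is no figure of its own to reproduce. The check compares the printed lists.

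**Step 1. UK lists as sets.** All distinct GPRD codes were entered from Appendix 1.

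- Antihypertensive block: 80 distinct codes.
- Diuretic block: 118 distinct codes.
- Codes in both blocks: 23, namely 4561, 4562, 4569, 4577, 4581, 4590, 4591, 4594, 4599, 4618, 5757, 5770, 5773, 6178, 6180, 6182, 6184, 6185, 6196, 6207, 6797, 6798 and 16704.

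**Step 2. Combinations in one block only.** The search covered codes that join a diuretic with one of the four antihypertensive classes of section 3.5.

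| Code | Content as shown in Appendix 1 | Antihypertensive block | Diuretic block | Counterpart |
|---|---|---|---|---|
| 4595 | Under the heading for angiotensin II inhibitors with diuretics | yes | no | 6207, same heading, in both |
| 4582 | Lisinopril with hydrochlorothiazide | no | yes | 4577, same ingredients, in both |
| 5758 | Pindolol with clopamide | no | yes | 5757, same ingredients, in both |
| 4556 | Propranolol with hydrochlorothiazide | no | yes | 6178, propranolol with another thiazide, in both |
| 4608 | Quinapril, in the group of thiazides with antihypertensives | no | yes | None; the quinapril code in the ACE-inhibitor list is 5776 |

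A sixth code, 6784 (ethacrynic acid with a branded product), is also in the diuretic block only. The protocol does not say what that brand contains, so it is left out of the count.

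The diuretic block also holds codes that combine a diuretic with reserpine, methyldopa, guanethidine, clonidine, hydralazine and similar drugs. These are outside the four classes in section 3.5, so counting them as diuretics only is consistent with the protocol.

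**Step 3. Share of codes.**

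Combination codes identifiable from the document = 23 + 5 = 28.

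In one block only = 5/28 = 17.9%, or about 18%.

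Of these five, four are missing from the antihypertensive block and one from the diuretic block.

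**Step 4. Denmark.** Overlap between {C07, C08, C09} and {C03} = 0 prefixes. With one ATC code per product, no product can set both covariates. The direction depends on where combinations are coded:

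- Coded under C07, C08 or C09: the antihypertensive covariate is set and the diuretic covariate is not. A patient whose only diuretic is in such a tablet is recorded as a non-user of diuretics.
- Coded under C03: the reverse.

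The protocol lists no Danish codes at product level, so the number of products affected cannot be computed.

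**Step 5. Who is misclassified.** Under the one-prescription rule, a UK patient gets the wrong value only if every prescription in the window that should set the covariate carries one of the codes missing from that block. One plain ACE inhibitor or beta-blocker, or one other listed diuretic, restores the relevant covariate. The protocol gives no prescription counts by code, so the share of patients cannot be derived.

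**The case against.** The best defence is that the protocol never promises to count each ingredient. That principle is inferred from the 23 overlapping codes, and a list need not follow an unstated rule. This is a fair remark about intent, but it does not explain why 4577 and 4582, or 5757 and 5758, are treated differently when their ingredients are the same. Whatever rule was meant, those pairs cannot both follow it.

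The second defence is that the practical effect may be negligible: the codes are few, the window can be long and one other qualifying prescription corrects the covariate. This stands and limits the weight of the point.

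Four stronger readings are tempting, and the document does not carry them:

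- **Six codes rather than five.** Counting 6784 would give 6/29 = 21%, but that needs knowledge of the brand's content from outside the protocol.
- **The percentage as a misclassification rate.** It is a share of code-list entries, not of prescriptions or patients.
- **A sensitivity for the Danish diuretic covariate.** If a share f of diuretic users took diuretics only in tablets coded under C07 to C09, sensitivity would be 1 − f; assuming f of 10% to 30% gives 90% to 70%. The result only restates the assumption, and nothing in the protocol anchors f.
- **Both covariates misclassified in both countries, so that the risk ratios are not comparable.** If Danish combinations are coded under C07 to C09, the antihypertensive covariate there is still set and only the diuretic covariate loses users. Section 3.6.3 plans no pooling or formal cross-country comparison of risk ratios. The quantitative Denmark–UK comparison in section 3.6.1 concerns utilisation trends, which do not use these covariates.

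**Conclusion.** Wrong as written, minor. In the UK lists, at least 5 of 28 antihypertensive–diuretic combination codes (18% of codes) set only one covariate while the other 23 set both. Four of the five lose the antihypertensive covariate and one loses the diuretic covariate. This can be verified from Appendix 1 alone.

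The Danish part is conditional. It assumes one ATC code per product, which fits section 6.1. The conclusion that the diuretic covariate is the one that loses users further assumes that combinations are coded under C07 to C09, which the protocol does not show.

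The number of patients affected is unknown in both countries and may be small. No effect on any risk ratio has been shown. The case for correcting the lists is that they are internally inconsistent and cheap to repair, not that a result is known to be biased.

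**What to change.** State one rule in section 3.5 for both countries: a fixed combination counts in every category to which one of its ingredients belongs. Then bring Appendix 1 into line.

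- **UK:** add 4595 to the diuretic list. Add 4556, 4582, 4608 and 5758 to the antihypertensive list. Add 6784 there as well if its content is confirmed to include a listed antihypertensive class.
- **Denmark:** let any product coded under C07, C08 or C09 that contains a diuretic also set the diuretic covariate, and any C03 product that contains a listed antihypertensive also set the antihypertensive covariate. The recorded ATC code and unique product number are the natural means of identifying these products.

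The cost is a code-list edit and one added sentence in section 3.5. No new data are needed.

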3.4 Endpoints

All codes relevant to abstracting diagnostic, drug, and laboratory data appear in Appendix 1.

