3.6.3 Acute drug reactions

For patient-level endpoints, baseline will be defined as the recorded date of medication switch/addition (as reflected by a new dispensation/issue); date of the first-time prescription dispensation/issue (in first-time users) or 1 January 2000 (in prevalent users).

We will examine the number of potential drug reactions occurring within 45 days of baseline and calculate the 45-day cumulative incidence of acute drug reactions, overall and diagnosis-specific (if the data set is large enough); We will estimate risk ratios for the acute drug reactions identified using regression, while adjusting for confounding.

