6782 CHLORTHALIDONE/POT.CHLORIDE
6150 RESERPIN,MEFRUSID,INOSITONICOT
4618 PERINDOPRIL + INDAPAMIDE
6752 CLOREXOLONE
6733 MERSALYL SODIUM
9198 PHENOBARBITAL W THEOBROMINE
4551 RESERPINE W FUROSEMIDE
6768 FUROSEMIDE W POTASSIUM
6793 (FUROSEMIDE W POTASSIUM
16704 FUROSEMIDE W PENBUTOLOL
6759 BUMETANIDE W POTASSIUM CHLORIDE
4605 PIRETANIDE
6790 TIENILIC ACID
6784 ETHACRYNIC ACID W TRASICOR
6766 ETOZOLIN
6781 LASIX W SPIRONOLACTON
6783 (SPIRONOLACTONE W HYDROCHLOROTHIAZID
6786 SPIRONOLACTONE W COMBINATIONS
16701 CHLOROTHIAZIDE W SPIRONOLACTONE
16702 CHLOROTHIAZIDE W SPIRONOLACTONE,LACTOSE

16708 POTASSIUM CANRENOATE
16712 EPLERENONE
4599 HYDROCHLOROTHIAZIDE+TIMOLOL+AMILORIDE
4616 TRIAMTERINE+AMILORIDE
16710 BUMETANIDE W AMILORIDE
4616 TRIAMTERINE+AMILORIDE
6765 BEMETIZIDE W TRIAMTERENE
6789 TRIAMTERINE W BENZTHIAZIDE

Nitrates

B06106 NITROGLYCERINE EXT.RELEASE
B06127 NITROGLYCERIN
B06167 NITROGLYCERIN + ISOSORBIDEDNITRAT
B06171 NITROGLYCERIN W COMBINATIONS
B06174 NITROGLYCERINE DISC
B06176 ISOSORBIDE MONONITRATE
B06206 ISOSORBIDE MONONITRATE+ASPIRIN
B06128 ISOSORBIDE DINITRATE
B06141 SODIUM NITROPRUSSIDE
B06153 AMYL NITRITE

Antiplatelet Agents

1923 EPOPROSTENOL
1928 ABCIXIMAB
1930 CLOPIDOGREL
5528 TICLOPIDIN
6105 DIPYRIDAMOLE
6201 DIPYRIDAMOLE 200MG/ASPIR
4979 Aloxiprin
1937 Tirofiban

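### The UK antiplatelet code list has no entry for aspirin alone, while Denmark uses the whole B01A group, so a named covariate is under-recorded in the UK and differs between countries

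*Protocol*

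**What the plan says.** Protocol section 3.5 lists five groups of co-medication as covariates, the last being "Antiplatelet agents". The rule for all five is the same: "Concomitant use will be defined as a record of at least one prescription for a medication" in the category, dated between the first and last glucose-lowering prescription.

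Section 3.4 makes the appendix the reference for codes: "All codes relevant to abstracting diagnostic, drug, and laboratory data appear in Appendix 1".

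In Appendix 1 the UK antiplatelet list contains epoprostenol, abciximab, clopidogrel, ticlopidin, dipyridamole, "6201 DIPYRIDAMOLE 200MG/ASPIR", "4979 Aloxiprin" and tirofiban. A further aspirin product, "B06206 ISOSORBIDE MONONITRATE+ASPIRIN", stands under Nitrates only.

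The Danish row for the same covariate, beginning "Antiplatelet agents (anti-thrombotic", gives the single code B01A.

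Section 3.6.3 estimates risk ratios for acute drug reactions by regression, "while adjusting for confounding". It does not itemise the adjustment set.

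**The concern.** Aspirin is an antiplatelet drug, and the UK list treats aspirin-type products as in scope, since it counts aloxiprin and the dipyridamole/aspirin combination. Yet a patient whose only antiplatelet prescription is plain aspirin meets no code on the list and is analysed as untreated. The protocol gives no reason for the omission.

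Antiplatelet prescribing plausibly marks known or suspected vascular disease. Such disease could influence both the decision to start or stop rosiglitazone and the 45-day events named in section 3.4.3, which include myocardial infarction, stroke and cardiovascular death. If recorded use misses many true users, adjusting for it removes only part of the confounding it was included to control. The limitations in section 4 mention residual confounding by lifestyle factors only, so a reader would not know of this gap.

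The Danish definition is wider by its own label. Risk ratios from the two countries would be described as adjusted for the same covariate when they are not.

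**Working it through.** **1. The lists side by side**

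| | UK (GPRD) | Denmark (prescription database) |
|---|---|---|
| Definition | 8 individual codes | whole group B01A |
| Aspirin alone | no code | not separately listed; only the group is given |
| Aspirin combinations | dipyridamole/aspirin counted; isosorbide mononitrate/aspirin under Nitrates only | not separately listed |
| Label | antiplatelet | antiplatelet, with anti-thrombotic in brackets |

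Elsewhere the UK appendix files combination products under each relevant class. Code 4598 (felodipine+ramipril) appears with both the ACE-inhibitor combinations and the calcium channel blockers. Code 4618 (perindopril+indapamide) appears with both the ACE-inhibitor combinations and the diuretics. B06206 departs from that practice.

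**2. Which database is affected**

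Section 3.3 gives about 2,400 rosiglitazone users in Denmark and about 20,000 in the GPRD. The GPRD share is 20,000 / (20,000 + 2,400) = 20,000 / 22,400 = 89%.

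**3. Illustration of size**

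The protocol gives no prevalence of antiplatelet use, no association with outcome and no capture rate, so there is no figure of its own to reproduce. Every input below is an assumption.

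*(a) Covariate left out entirely, nothing else adjusted.* Let p1 and p0 be true antiplatelet use in the two compared groups, and R the risk ratio of users against non-users for the outcome. Then

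bias factor = [1 + p1(R − 1)] / [1 + p0(R − 1)]

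| p1 vs p0 | R = 1.5 | R = 2 | R = 3 |
|---|---|---|---|
| 40% vs 30% | 1.20/1.15 = 1.04 | 1.40/1.30 = 1.08 | 1.80/1.60 = 1.13 |
| 50% vs 30% | 1.25/1.15 = 1.09 | 1.50/1.30 = 1.15 | 2.00/1.60 = 1.25 |

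This gives 4–13% in the first case and 9–25% in the second.

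*(b) Covariate included but under-recorded.* Suppose the code list captures a share s of true users in both groups, with no false positives, and the true exposure risk ratio is 1. Among those recorded as non-users, the share who are really users is q1 = p1(1 − s)/(1 − p1·s) in the exposed, and q0 likewise in the unexposed. Standardised to the exposed,

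adjusted RR = [p1·s·R + (1 − p1·s)(1 + q1(R − 1))] / [p1·s·R + (1 − p1·s)(1 + q0(R − 1))]

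Here the exposed are taken to have the lower use, so the bias runs below 1; the documents do not settle the direction. One case in full: p1 = 0.3, p0 = 0.5, R = 3, s = 0.1.

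- q1 = 0.27/0.97 = 0.278 and q0 = 0.45/0.95 = 0.474.
- Numerator: 0.03 × 3 + 0.97 × (1 + 0.278 × 2) = 1.60.
- Denominator: 0.03 × 3 + 0.97 × (1 + 0.474 × 2) = 1.98.
- Adjusted RR = 0.81, against an unadjusted RR of 1.6/2.0 = 0.80.
- Share of the log-bias left: ln 0.809 / ln 0.800 = 0.95.

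Across 30% vs 40%, 40% vs 50% and 30% vs 50%, with R of 1.5, 2 and 3:

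- unadjusted RR: 0.80 to 0.96;
- adjusted RR with s between 10% and 40%: 0.81 to 0.97;
- share of the log-bias from this variable that remains: about 72% to 95%;
- adjusted RR with s = 100%: 1.00. This holds by construction, because the model has one confounder and a true RR of 1.

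**The case against.** The case against rests on what is inferred from the lists, not on what they contain.

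**Size.** A reader might infer that antiplatelet use is a main marker of cardiovascular risk here, that most UK users are misclassified, and that adjustment therefore achieves little. The protocol supports none of these: it gives no aspirin or antiplatelet prevalence and does not rank its covariates. This objection stands.

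**Other adjustment.** The 4–25% assumes the variable is omitted and nothing else is adjusted. Section 3.5 also lists a Charlson index, which contains myocardial infarction, heart failure, peripheral vascular and cerebrovascular disease, together with statins, antihypertensives, diuretics and nitrates. Section 3.4.3 also limits outcomes to first-onset events. Much of the vascular disease that antiplatelet use would stand for is thus measured in other ways. This stands, and makes the range a high illustration.

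**Countries.** A reader might infer that the mismatch biases the results. No pooled risk ratio is planned, and the quantitative comparison of Denmark with the UK in section 3.6.1 concerns prescribing trends. The mismatch limits comparability and does not by itself bias either country's estimate. This stands.

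**Adjustment set.** Section 3.6.3 leaves the model terms open, and a separate analysis plan may choose among the covariates. This stands for the model. It does not extend to the code list, which section 3.4 places in this document.

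**Timing.** Section 3.5 counts any prescription between the first and last glucose-lowering prescription, so treatment begun after a 45-day event also counts. Adding aspirin to a covariate timed that way could add adjustment for a consequence of the event. This is a separate weakness that a code edit does not cure, and it does not justify the incomplete list.

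**Conclusion.** The point holds as a code-list defect of minor weight. By the protocol's own rules, UK patients prescribed only aspirin are non-users of a covariate the protocol names, in the source with 89% of the rosiglitazone users. Under the same name Denmark uses a group that is wider by its label.

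An unknown, possibly large, share of UK antiplatelet users is misclassified. If the covariate enters the model, some residual confounding is left in the adjusted 45-day risk ratios. Neither its size nor its direction can be derived from the documents. The 4–25% illustrates assumed prevalences of 40% or 50% against 30% and outcome risk ratios of 1.5 to 3 with no other adjustment; the planned covariates would absorb part of it. The 72–95% depends on an assumed capture of 10–40%.

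The descriptive aims on utilisation, contraindicated use and off-label use do not use this covariate and are unaffected.

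**What to change.** In Appendix 1:

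- add the GPRD code or codes for prescribed aspirin alone to the UK antiplatelet list;
- cross-list B06206 there, keeping it under Nitrates as well;
- replace B01A in the Danish table with the antiplatelet codes within that group, so that both countries apply one definition. If the difference is intended, state why.

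The cost is an edit to two code lists before extraction. Section 6.2 says the Drug File covers all drugs prescribed by the GP, so no new UK data are needed. The downside is that aspirin bought without prescription stays uncaptured; the limitations in section 4 should say so.
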